#### **13.4. ECG**

A 12-lead, resting ECG will be obtained at the visits indicated in the Schedule of Assessments ([Table 1](#)). Summary statistics for actual values and changes from baseline will be provided for each of the ECG parameters at each scheduled visits, including ventricular rate (bpm), PR (msec), QRS (msec), QT (msec), and QTcF (msec) measurements will be obtained. A frequency table with number of percentage of patients with normal, abnormal and clinically significant abnormal ECG results will be provided. The clinically noteworthy QT/QTc interval (>450, >480, or >500 msec) or clinically noteworthy change from baseline (>30 or >60 msec) will also be summarized using frequency tables by treatment group at each scheduled visit.

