The potential risks of ME3183 can be estimated based on the AE profile of apremilast (a PDE4 inhibitor) presented in the commercial labeling. The common AEs include diarrhea, nausea, vomiting, depression, weight decrease, upper respiratory tract infection, nasopharyngitis, abdominal pain upper, and headache (Otezla package insert, USA, revised: 04/2020). Also, the most common side effects of known oral PDE4 inhibitors are gastrointestinal (GI) effects such as nausea, vomiting, and diarrhea.⁽⁷⁾ Additionally, GI motility disorder, inflammatory findings including arteritis/vasculitis, and QTc prolongation were reported based on the nonclinical studies.

The potential side effects identified in ME3183 nonclinical studies and also in studies involving other oral PDE4 inhibitors will be carefully monitored in the current study. The GI motility disorder will be identified by monitoring the subjects for any signs of abdominal discomfort,

abdominal distension, abdominal pain, nausea, vomiting, loss of appetite, and constipation. Besides the above, all subjects will be monitored for any cardiovascular manifestations using vital signs and 12-lead electrocardiograms (ECGs). Drug class potential effects such as weight loss and major depression will be monitored during this study. Weight will be measured at scheduled visits throughout the study to check for any potential excessive weight loss. Subjects with major depression or at risk for suicide will be excluded and suicidal ideation will be assessed at Screening and/or Baseline by Columbia-Suicide Severity Rating Scale (C-SSRS).

Considering the above safety profile of ME3183, caution will be exercised (investigator's judgement) before randomizing subjects with any clinically significant (CS) comorbidities (cardiovascular, GI, neurological, etc.). See [Section 8](#) for detailed list of inclusion and exclusion criteria.

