10.2 Study Procedures

Assessments and their timing are to be performed as outlined in the Schedule of Assessments (Table 1). Section 12.5 specifies safety laboratory assessment samples to be obtained.

Assessments and procedures scheduled should be performed before administration of treatment unless otherwise indicated in the Schedule of Assessments (Table 1).

Efficacy assessments are described in Section 11 and include PASI, sPGA, BSA, itch NRS, and DLQI scoring.

Safety assessments are described in Section 12 and include demographics, medical history, vital signs (including body temperature, body weight, respiratory rate, heart rate, and systolic and diastolic blood pressure measurements), complete/targeted physical examinations, ECGs, safety laboratory assessments (hematology, coagulation, chemistry, urinalysis, viral serology, pregnancy tests, and serum follicle-stimulating hormone tests), and AEs.

PK and CCI sampling is described in Section 13 and Section 14.1, respectively.

Other assessments such as medical photography of affected skin area and C-SSRS are described in Section 14.2 and Section 14.3, respectively.

The investigator may, at his/her discretion, arrange for a subject to have an unscheduled assessment, especially in the case of AEs that require follow-up or are considered by the investigator to be possibly related to the use of study drug. The unscheduled visit page in the eCRF must be completed.

Study discontinuation procedures are described in Section 8.4.

The procedures to be performed during each study visit are provided in Schedule of Assessments (Table 1).

A follow-up visit is performed at the clinical study site 4 weeks after the last dose of study drug.

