12.4 Electrocardiograms

A 12-lead, resting ECG will be obtained at the visits indicated in the Schedule of Assessments ([Table 1](#)). During the ECG, ventricular rate (bpm), PR (msec), QRS (msec), QT (msec), and QTcF (msec) measurements will be obtained.

All the ECGs obtained will be interpreted by an experienced single independent blinded reader at the central laboratory.

At Screening, the investigator will examine the ECG traces for signs of cardiac disease that could exclude the subject from the study (QTcF >450 msec). An assessment of normal or abnormal will be recorded; if the ECG is considered abnormal, the abnormality will be documented in the eCRF. ECGs will be repeated if CS abnormalities are observed, or artifacts are present. The date and time of each ECG and its results will be documented in the source documents and eCRF.

Any CS ECG abnormalities must be recorded as AEs.

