15.4 Safety Analyses

All safety analyses will be performed using the safety analysis set. All recorded AE and SAEs will be listed and tabulated by Medical Dictionary for Regulatory Activities (version 24.1 or higher) system organ class, preferred term, and treatment group over the 16-week Treatment Period and the 4-week Follow-up Period.

The incidence of TEAEs (events with onset dates on or after the first dose of the study drug or that was present prior to dosing and exacerbates after the first dose of study drug) will be included in incidence tables. Events with missing onset dates will be included as TEAEs. If a subject experiences more than 1 occurrence of the same AE, the occurrence with the greatest severity and the closest association with the study drug will be used in the summary tables. SAEs and AEs causing study discontinuation will be tabulated. All AEs will be listed by subject, along with information regarding onset, duration, relationship and severity to study drug, seriousness, action taken with study drug, treatment of event, and outcome.

Vital signs and safety laboratory results will be listed and summarized by treatment group over the 16-week Treatment Period and the 4-week Follow-up Period. Summaries will be provided using descriptive statistics, including mean values and mean change from Baseline values, as well as numbers of subjects with values outside limits of the normal range at each time point.

Any CS physical examination findings and safety laboratory results will be summarized. ECG readings will be evaluated by the investigator and abnormalities, if present, will be summarized and listed. The clinically noteworthy QT/QTc interval (> 450 , > 480 , or > 500 msec) or clinically noteworthy change from Baseline (> 30 or > 60 msec) will also be summarized using descriptive statistics.

Summary tables will be provided for concomitant medications initiated during the study period.

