14.3.1.7	Treatment-Emergent Adverse Events Leading to Permanent Discontinuation of Study Drug by System Organ Class and Preferred Term	(Safety Analysis Set)
14.3.1.8	Treatment-Emergent Adverse Events by Time of Onset, System Organ Class and Preferred Term	(Safety Analysis Set)

This document is confidential.

Table Number	Name	Analysis Set
14.3.2.1	Serious Treatment-Emergent Adverse Events, Listing	(Safety Analysis Set)
14.3.2.2	Treatment-Emergent Adverse Events Leading to permanent Discontinuation of Study Drug, Listing	(Safety Analysis Set)
14.3.4.1.1.1	Hematology and Coagulation: Summary by Visit and Change from Baseline	(Safety Analysis Set)
14.3.4.1.1.2	Hematology and Coagulation: Proportion of Abnormal Results by Study Visit	(Safety Analysis Set)
14.3.4.1.2.1	Blood Chemistry: Summary by Visit and Change from Baseline	(Safety Analysis Set)
14.3.4.1.2.2	Blood Chemistry: Proportion of Abnormal Results by Study Visit	(Safety Analysis Set)
14.3.4.1.3	Urinalysis: Proportion of Abnormal Results by Study Visit	(Safety Analysis Set)
14.3.4.2	Summary of Vital Signs by Visit and Change from Baseline	(Safety Analysis Set)
14.3.4.3.1	12-Lead ECG: Summary by Visit and Change from Baseline	(Safety Analysis Set)
14.3.4.3.2	12-Lead ECG: Summary of Overall ECG Interpretation by Visit	(Safety Analysis Set)
14.3.4.3.3	12-Lead ECG: Summary of Noteworthy Changes of QT/QTc Interval by Visit	(Safety Analysis Set)

This document is confidential.

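### QTc outliers are summarised only by scheduled visit: unscheduled ECGs fall outside the table, repeats have no rule, and no count of subjects with any post-baseline outlier is provided

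*SAP*

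**What the plan says.** **Analysis.** SAP 13.4 sets the categories: "The clinically noteworthy QT/QTc interval (>450, >480, or >500 msec) or clinically noteworthy change from baseline (>30 or >60 msec"). It says that these "will also be summarized using frequency tables by treatment group at each scheduled visit". SAP section 18 indexes one table for this, 14.3.4.3.3, titled "12-Lead ECG: Summary of Noteworthy Changes of QT/QTc Interval by Visit". The other ECG frequency table, 14.3.4.3.2, is "12-Lead ECG: Summary of Overall ECG Interpretation by Visit"; it covers the overall reading, not the QTc thresholds. Protocol 15.4 says of the same categories only that they "will also be summarized using descriptive statistics", with no restriction to scheduled visits and no subject-level rule.

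**Off-schedule tracings.** Protocol 12.4 foresees repeats: "ECGs will be repeated if CS abnormalities are observed, or artifacts are present". Protocol 10.2 lets the investigator "arrange for a subject to have an unscheduled assessment", which is recorded on its own eCRF page. SAP 8.4 analyses visits as they stand in the database and does not re-window them by date.

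**Why QTc is singled out.** Among the potential risks, Protocol 5.3 lists GI motility disorder, arteritis/vasculitis "and QTc prolongation were reported based on the nonclinical studies". Protocol 8.4 includes QTcF above 500 msec among the reasons for which a subject may be withdrawn.

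**The concern.** For a pre-identified risk, the basic safety question in each group is how many subjects ever crossed a threshold, compared with placebo. A by-visit table answers a different question: how many were over the threshold on a given scheduled day. The same small count at every visit may be one subject with a persistent finding or a different subject each time, and these mean different things for the drug.

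The second problem is which tracings enter. An ECG taken off schedule, for instance to follow up an adverse event, belongs to no scheduled visit and so to no row. Where a visit holds an initial tracing and a repeat, the SAP does not say whether the first, the last, the mean or the largest value is tabulated. Two programmers could produce different outlier counts from the same data.

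At stake is the summary of a named safety risk in the first study of this drug in patients. No efficacy analysis is involved.

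**Working it through.** The documents give no figure for QTc outliers, so there is nothing to reproduce. The check has two parts.

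**1. Does any planned table give the subject-level count?**

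| Place | What it provides | Gives subjects with any QTc outlier? |
|---|---|---|
| SAP 13.4 text | Threshold counts at each scheduled visit | No |
| Table 14.3.4.3.3 | Same, by visit | No |
| Table 14.3.4.3.2 | Overall ECG interpretation, by visit | No; not threshold-based |
| SAP 7.3 | Per-subject variable for abnormal ECG findings | No; not threshold-based, and no any-visit table is indexed for it |
| AE tables | Abnormalities judged clinically significant and recorded as AEs | No; investigator judgement, not thresholds |
| Listing 16.2.8.2.2 | Individual ECG data, indexed on the FAS | Only by hand count |

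Unscheduled ECGs have their own eCRF page (Protocol 10.2). Because SAP 8.4 does not re-assign visits, they cannot move into a scheduled-visit row.

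**2. How much do by-visit counts leave open?**

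Inputs:
- n = 25 subjects per group (Protocol 7.1; SAP 4.1).
- V = 5 scheduled post-baseline ECG visits: Weeks 4, 8, 12, 16 and 20 (Schedule of Assessments). Of these, 4 are on-treatment visits (Weeks 4 to 16).
- k = outliers seen at each visit. This is an assumption; the documents give no rate. For simplicity every subject is taken to have an ECG at every visit.

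If k subjects are over a threshold at each of V visits, the number with at least one outlier is smallest when they are always the same subjects, and largest when they are all different:

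k ≤ subjects with any outlier ≤ min(n, k × V)

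| k per visit | Lowest | Highest, V = 4 | Highest, V = 5 |
|---|---|---|---|
| 1 (4%) | 1/25 = 4% | 4/25 = 16% | 5/25 = 20% |
| 2 (8%) | 2/25 = 8% | 8/25 = 32% | 10/25 = 40% |
| 3 (12%) | 3/25 = 12% | 12/25 = 48% | 15/25 = 60% |

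If crossings were independent between visits with probability 0.04 each, the chance of at least one would be 1 − 0.96^5 = 18.5% over five visits, or 1 − 0.96^4 = 15.1% over four. This is only a reference point: a subject's QTcF values are likely to be correlated over time, which would pull the figure towards the lower bound.

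The assumed k sets the width of the range. That by-visit counts do not determine the subject-level count does not depend on k.

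**The case against.** The other side has real points.

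- **Repeats are not excluded.** A reader might infer that repeat ECGs enter no table. The documents do not support that. A repeat made at a scheduled visit may be recorded under that visit, and SAP 8.4 uses visits as recorded. What is missing is a rule for which value counts. Only ECGs recorded as unscheduled clearly fall outside.
- **Repeats are not only for abnormal tracings.** Protocol 12.4 also calls for them when there is artifact. A worst-value summary that ignored this could count artifacts as outliers, so the fix has to deal with it.
- **The data are not lost.** A reader might infer that the most abnormal tracing could vanish from the report. Clinically significant ECG abnormalities must be recorded as AEs, withdrawals are summarised by primary reason, and SAP 8.1 promises listings of all subject data. With about 25 subjects per group, a hand count is feasible. The ECG listing is indexed on the FAS, which requires an evaluable post-baseline PASI. That should drop few subjects, because PASI starts at Week 1, before the first post-baseline ECG at Week 4. Still, AE reporting turns on judgement, and a hand count is not a planned summary.
- **The shells were not available.** SAP section 21 places them in a separate document, and an any-post-baseline row there cannot be ruled out. The finding is therefore about the SAP text and table index, neither of which calls for such a row.
- **No requirement is breached.** Protocol 15.4 asks only for descriptive statistics, and this is a proof-of-concept study without a formal sample size calculation. That limits the weight of the point but does not supply the missing count.

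**Conclusion.** The point holds as a gap in safety reporting. Followed as written, the SAP yields QT/QTc outlier counts by scheduled visit, leaves out ECGs recorded as unscheduled, has no rule for repeats within a visit, and gives no number of subjects with any post-baseline outlier.

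The size can only be illustrated. At an assumed one outlier per visit, the subject-level figure could be anywhere from 4% to 20% of a group over the five post-baseline visits, or 4% to 16% on treatment. This assumes 25 subjects per group with complete ECGs. It is not a forecast, and the upper end requires a different subject at every visit.

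The documents do not show that QTc data would go uncollected or unlisted, or that repeats are barred from the tables. The change is worth making because the risk is named in the protocol and the remedy is cheap; the efficacy conclusions do not depend on it.

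**What to change.** Amend SAP 13.4 and Table 14.3.4.3.3 as follows.

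1. Add a worst-post-baseline block on the Safety Analysis Set, by treatment group. Count each subject once by maximum QTcF (>450, >480, >500 msec) and once by maximum increase from baseline (>30, >60 msec).
2. Use all scheduled, repeat and unscheduled post-baseline ECGs for the maximum, except tracings replaced because of artifact. The replaced tracing has to be identifiable in the ECG data; confirm this before programming.
3. Keep the by-visit rows, and state which value they use when a visit has more than one ECG.
4. If the shells already contain such a block, bring the SAP text and table title into line with them.

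The cost is one extra table block from data already collected. The downside is that a maximum over more tracings gives somewhat higher counts in every group, placebo included, so the block should be read as a comparison with placebo and not as an absolute rate.

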#### **13.5. Physical Examination**

A complete physical examination including height and weight will be performed at Screening (Visit 1). A targeted physical examination to verify continued subject eligibility and to follow-up regarding any change in medical history will be performed at the study visits indicated in Schedule of Assessments ([Table 1](#)). Symptom-driven, targeted physical examinations will be performed as clinically indicated at any study visit. Any CS physical examination finding should be reported as an AE. All physical examination data will be summarized in data listings.

This document is confidential.

## **14. Changes from Analysis Planned in Protocol**

There are no changes from analysis planned in the study protocol.

This document is confidential.

## 16. Programming Considerations

- All TFLs, and statistical analyses will be generated using SAS Version 9.4 (SAS Institute Inc., Cary, NC, USA). Computer-generated TFL outputs will adhere to the following specifications.

### 16.1. General Considerations

- One SAS program can create several outputs, or a separate SAS program will be created for each output.
- One output file can contain several outputs or each output will be stored in a separate file.
- Output files will be delivered in Word format or portable document format pdf.
- Numbering of TFLs will follow International Council for Harmonisation (ICH) E3 guidance.

### 16.2. Table, Figure, and Listing Format

#### 16.2.1. General

- All TFLs will be produced in landscape format on <American letter size / A4 paper size>, unless otherwise specified.
- All TFLs will be produced using the Courier New font, size 8 which is the smallest acceptable point size for the Regulatory Authorities.
- The data displays for TFLs will have a minimum blank 1-inch margin on all 4 sides.
- Headers and footers for figures will be in Courier New font, size 8 which is the smallest acceptable point size for the Regulatory Authorities.
- Legends will be used for all figures with more than one variable, group, or item displayed.
- TFLs will be in black and white (no color), unless otherwise specified.
- Specialized text styles, such as bolding, italics, borders, shading, and superscripted and subscripted text, will not be used in the TFLs, unless otherwise specified. On some occasions, superscripts 1, 2, or 3 may be used.
- Only standard keyboard characters will be used in the TFLs. Special characters, such as non-printable control characters, printer-specific, or font-specific characters, will not be used. Hexadecimal-derived characters will be used, where possible, if they are appropriate to help display math symbols (e.g.,  $\mu$ ). Certain subscripts and superscripts (e.g.,  $cm^2$ ,  $C_{max}$ ) will be employed on a case-by-case basis.
- Mixed case will be used for all titles, footnotes, column headers, and programmer-supplied formats, as appropriate.

#### 16.2.2. Headers

All outputs will have the following header at the top left of each page:

- Meiji Pharma USA Inc.

This document is confidential.

- Protocol ME3183-3 (PPD) Study Number 7028898)
- Draft/Final Run: <ddmmmyyyy>
- All outputs will have Page n of N at the top or bottom right corner of each page. TFLs are internally paginated in relation to the total length (i.e., the page number will appear sequentially as page n of N, where N is the total number of pages in the table).
- The date the output was generated will appear along with the program name as a footer on each page.

#### 16.2.3. Display Titles

- Each TFL will be identified by the designation and a numeral (i.e., Table 14.1.1). A decimal system (x.y and x.y.z) are used to identify TFLs with related contents. The title will be centered. The analysis set will be identified on the line immediately following the title and will be enclosed in parenthesis. The title and table designation will be single spaced. A solid line spanning the margins will separate the display titles from the Column headers. There will be one blank line between the last title and the solid line.

Table x.y.z  
First Line of Title  
Second Line of Title if Needed  
(ITT Analysis Set)

#### 16.2.4. Column Headers

- Column headings will be displayed immediately below the solid line described above in initial upper-case characters.
- In the case of efficacy tables, the variable (or characteristic) column is on the far left followed by the treatment group columns and total column (if applicable). P-values may be presented under the total column or in separate p-value column (if applicable). Within-treatment comparisons may have p-values presented in a row beneath the summary statistics for that treatment.
- For numeric variables, include 'unit' in column or row heading when appropriate.
- Analysis set sizes will be presented for each treatment group in the column heading as (N=xx) (or in the row headings, if applicable). This is distinct from the 'n' used for the descriptive statistics representing the number of subjects in the analysis set.
- The order of treatments in the tables and listings will be Placebo first in the case of placebo controlled studies and Active comparators first in the case of active comparator trials, followed by a total column (if applicable).

#### 16.2.5. Body of the Data Display

##### 16.2.5.1. General Conventions

Data in columns of a table or listing are formatted as follows:

This document is confidential.

- Alphanumeric values will be left-justified;
- Whole numbers (e.g., counts) will be right-justified; and
- Numbers containing fractional portions will be decimal aligned.

#### 16.2.5.2. Table Conventions

- Units will be included where available.
- For categorical parameters, all categories will be presented in the table, even if n=0 for all treatment groups in a given category. For example, the frequency distribution for symptom severity would appear as:

Severity Rating	N
severe	0
moderate	8
mild	3

Where percentages are presented in these tables, zero percentages will not be presented and so counts of 0 will be presented as 0 and not as 0 (0%).

- An Unknown or Missing category will be added to each parameter for which information is not available for 1 or more subjects.
- Unless otherwise specified, the estimated mean and median for a set of values will be printed out to 1 more significant digit than the original values, and standard deviations will be printed out to 2 more significant digits than the original values. The minimum and maximum will report the same significant digits as the original values. For example, systolic blood pressure will be presented as follows:

N	XX
Mean	XXX.X
Std Dev	X.XX
Median	XXX.X
Minimum	XXX
Maximum	XXX

- P-values will be output in the format: '0.xxx', where xxx is the value rounded to 3 decimal places. Every p-value less than 0.001 will be presented as <0.001. If the p-value are less than 0.0001, then present as <0.0001. If the p-value is returned as >0.999, then present as >0.999.
- Percentage values will be printed to one decimal place, in parentheses with no spaces, one space after the count (e.g., 7 (12.8%), 13 (5.4%)). Unless otherwise noted, for all percentages, the number of subjects in the analysis set for the treatment group who have an observation will be the denominator. Percentages after zero counts will not be displayed and percentages equating to 100% will be presented as 100%, without decimal places.

This document is confidential.

- Tabular display of data for medical history, prior/concomitant medications, and all tabular displays of adverse event data will be presented by the body system, treatment class, or SOC with the highest occurrence overall in decreasing order, assuming all terms are coded. Within the body system, drug class and SOC, medical history (by preferred term), drugs (by ATC1 code), and adverse events (by preferred term) will be displayed in decreasing order. If incidence for more than 1 term is identical, they will then be sorted alphabetically. Missing descriptive statistics or p-values which cannot be estimated will be reported as '-'.
- The percentage of subjects will normally be calculated as a proportion of the number of subjects assessed in the relevant treatment group (or overall) for the analysis set presented. However, careful consideration is required in many instances due to the complicated nature of selecting the denominator, usually the appropriate number of subjects exposed. Details will be described in footnotes or programming notes, as necessary.
- For categorical summaries (number and percentage of subjects) where a subject can be included in more than one category, a footnote or programming note will be added describing whether the subject is included in the summary statistics for all relevant categories or just 1 category as well as the selection criteria.
- Where a category with a subheading (such as SOC) has to be split over more than one page, output the subheading followed by '(cont)' at the top of each subsequent page. The overall summary statistics for the subheading should only be output on the first relevant page.

